9. History of brain involvement with cancer, spinal cord compression, or carcinomatous meningitis, or new evidence of brain or leptomeningeal disease. Patients with radiated or

- resected lesions are permitted, provided the lesions are fully treated and inactive, patients are asymptomatic, and no steroids have been administered for at least 28 days.
10. Angina, MI, symptomatic congestive heart failure, cerebrovascular accident, transient ischemic attack, arterial embolism, pulmonary embolism, PTCA or CABG within the past 6 months. Deep venous thrombosis within 6 months unless the patient is anticoagulated without the use of warfarin for at least 2 weeks. In this situation, low molecular weight heparin is preferred.
 11. Active bleeding or pathologic condition that carries a high risk of bleeding (e.g. hereditary hemorrhagic telangiectasia).
 12. Thrombolytic use (except to maintain i.v. catheters) within 10 days prior to first day of study therapy
 13. Known active viral or nonviral hepatitis or cirrhosis
 14. History of hemorrhage or hemoptysis (> ½ teaspoon bright red blood) within 3 months of starting study treatment
 15. History of peptic ulcer disease within 3 months of treatment, unless treated for the condition and complete resolution has been documented by esophagogastroduodenoscopy (EGD) within 28 days of starting study treatment
 16. History of gastrointestinal perforation or fistula in the past 6 months, or while previously on antiangiogenic therapy, unless underlying risk has been resolved (e.g., through surgical resection or repair)
 17. Known human immunodeficiency virus (HIV) or acquired immunodeficiency syndrome (AIDS) related illness
 18. Receipt of a strong CYP3A4/5 inducer within 12 days prior to cycle 1 day 1 or a strong CYP3A4/5 inhibitor within 7 days prior to cycle 1 day 1 ([Table 18](#))
 19. Other severe acute or chronic medical (including bone marrow suppressive diseases) or psychiatric condition or laboratory abnormality that may increase the risk associated with study participation or may interfere with the interpretation of study results and, in the judgment of the Investigator, would make the patient inappropriate for this study
 20. Patients with known hypersensitivity to Chinese hamster ovary products or other recombinant human, chimeric, or humanized antibodies
 21. Significant ascites or pericardial or pleural effusion

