2.3.6. Potential Risks and Benefits to Human Patients

2.3.6.1. Potential Risks

TRC105

Grade 3 anemia has occurred with TRC105 therapy at the recommended phase 2 dose. All patients treated with TRC105 should be monitored closely for anemia and treated appropriately, including the possibility of TRC105 dose reductions. Anemia may be caused by correctable mineral or vitamin deficiency. The anemia related to TRC105 is hypoproliferative in nature and is reversible with interruption of treatment, transfusion, erythropoietin, and other interventions as appropriate.

Gastrointestinal hemorrhage has occurred with TRC105 therapy. Patients with active ulcer disease or risk factors for ulcer disease are excluded from this study.

Grade 1 and 2 cutaneous telangiectasia related to TRC105 occur early in the course of therapy and have been the source of gingival bleeding and epistaxis. Telangiectasia are also seen in patients with hereditary hemorrhagic telangiectasia (HHT), a disease of CD105 haplotype insufficiency. Patients with HHT are at risk of hemorrhage from abnormal blood vessels and this could be exacerbated by treatment with TRC105. Other contraindications to TRC105 therapy include a history of significant hemorrhage or tumors located in the central chest or another location where bleeding is associated with high morbidity. All patients treated with TRC105 should be monitored for signs of hemorrhage and the risks and benefits of drug treatment reevaluated in any patient with hemorrhage.

Premedication including the use of glucocorticoid is required prior to infusion of TRC105 to reduce the frequency and severity of infusion reactions. Infusion reactions following TRC105 dosing generally occur with the first TRC105 dose and include a grade 4 vasovagal reaction that resolved without sequelae. Signs and symptoms of TRC105 infusion reactions include hypertension, hypotension, dyspnea, bronchospasm, chills/rigors, chills, sweats, fever, nausea, tachycardia, bradycardia, EKG changes, flushing, urticaria, pruritus, and headache, generally of

grade 1 and 2 severity. Potential infusion reactions seen with other therapeutic antibodies include angioedema, asthenia, throat irritation, rhinitis, vomiting, joint pain, fatigue and neurologic disorders including inflammation of the spine and/or brain.

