Hypersensitivity reactions with infusions are a potential risk for sensitized patients, and TRC105 should be used with caution in patients with known hypersensitivity to any component of the drug product. Host anti-TRC105 antibodies to the murine or human portions of CHO-produced TRC105 are rare. In general, the risk of immunogenicity to therapeutic chimeric antibodies is small (<10%) and the clinical significance of immunogenicity is not well defined. The current trial will collect serial blood samples for anti-product antibody concentrations to further characterize the immunogenicity of TRC105 and potential clinical implications.

Grade 3 cerebrovascular hemorrhage resulting in hemiparesis occurred in one patient with hepatocellular cancer who was thrombocytopenic (who entered the study with a platelet count of 60,000/uL) in a study of TRC105 with sorafenib. Patients must have a platelet count of > 100,000/uL to enter this study (see inclusion criteria). A grade 2 transient ischemic attack was reported in a study of TRC105 and pazopanib. Grade 3 pancreatitis was also observed in this study. Transient Grade 3 hepatic encephalopathy occurred in one patient with cirrhosis and hepatocellular carcinoma who received TRC105 in combination with sorafenib. Additionally, Grade 5 intracranial hemorrhage occurred in one glioblastoma patient with markedly abnormal blood clotting parameters in a study of TRC105 with bevacizumab. A patient with glioblastoma developed temporary confusion and slurred speech following treatment with TRC105 and bevacizumab that required hospitalization for observation. Another patient with glioblastoma, who underwent resection and had a history of an abnormal collection of cerebral spinal fluid, developed a grade 2 cerebral spinal fluid leak. A third patient with glioblastoma and history of recurrent meningitis developed recurrent grade 3 bacterial meningitis while treated with bevacizumab and TRC105.

Grade 3 myocardial infarction (non-Q wave infarct associated with hypertension following an infusion reaction) was observed in a patient with hepatocellular cancer following treatment with TRC105 that resolved without sequelae. Patients with evidence of active coronary artery disease are excluded from participation in this trial (see exclusion criteria).

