Co-administration of rifampin, a strong inducer of CYP3A4/5, reduced the plasma exposure of axitinib in healthy volunteers. Co-administration of axitinib with strong CYP3A4/5 inducers (e.g., rifampin, dexamethasone, phenytoin, carbamazepine, rifabutin, rifapentin, phenobarbital, and St. John's wort) should be avoided. Selection of concomitant medication with no or minimal CYP3A4/5 induction potential is recommended. Moderate CYP3A4/5 inducers (e.g., bosentan, efavirenz, etravirine, modafinil, and nafcillin) may also reduce the plasma exposure of axitinib and should be avoided if possible.

Table 18: Strong CYP3A4/5 Inducers and Inhibitors

Inducers:	^aInhibitors:	
dexamethasone	Boceprevir	Conivaptan
phenytoin	Indinavir	Itraconazole
carbamazepine	Nelfinavir	Ketoconazole
rifampin	Lopinavir/ritonavir	Mibefradil
rifabutin	Saquinavir	Nefazodone
rifapentin	Telaprevir	Posaconazole
phenobarbital	Ritonavir	Voriconazole
St. John's Wort	Clarithromycin	Telithromycin

^a Because the lists of these agents are constantly changing, it is important to regularly consult a comprehensive list such as the one located at <http://medicine.iupui.edu/clinpharm/ddis/>.

Patients with arterial thrombosis or grade 3 or 4 venous thrombosis should be removed from study. Patients with grade 1 or 2 venous thrombosis who require anticoagulation will have their TRC105 therapy interrupted. TRC105 therapy may resume once the following criteria are met:

- The patient is on a stable dose of heparin or low molecular weight heparin or Factor X inhibitor.
- The patient has a platelet count > 100,000.
- The patient has not had a hemorrhagic event of grade 2 or higher while on study.
- The patient does not have a pathological condition that carries a high risk of bleeding (e.g., tumor involving major vessels).
- The patient is benefiting from TRC105 therapy (no evidence of disease progression).

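### Section 2.3.6.1 says patients with ulcer risk factors are excluded, but no criterion excludes them; its tumor-site contraindication is only partly carried into the entry criteria

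*Protocol*

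**What the plan says.** **Ulcer risk.** Protocol Section 2.3.6.1, after noting that gastrointestinal hemorrhage has occurred on TRC105, states: "Patients with active ulcer disease or risk factors for ulcer disease are excluded from this study". The only ulcer criterion is exclusion 15 (Synopsis, repeated in Section 5.1.2): "History of peptic ulcer disease within 3 months of treatment, unless treated for the condition and complete resolution has been documented by" endoscopy within 28 days of starting treatment. Section 6.3 lets NSAIDs be offered for pain or headache and asks for an H2 blocker or proton pump blocker once on-study use exceeds three days in a row.

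Section 2.3.1.3 reports that, in the phase 1 monotherapy study, one patient had a grade 4 bleed from a gastric ulcer within 5 days of the first infusion at 0.1 mg/kg. That protocol was then amended to exclude patients with an ulcer history (unless healing was documented) and patients on ulcerogenic medications, NSAIDs included.

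**Tumor site.** Section 2.3.6.1 also says: "Other contraindications to TRC105 therapy include a history of significant hemorrhage or tumors located in the central chest or another location where bleeding is associated" (the sentence goes on to specify high morbidity). Exclusion 11 reads: "Active bleeding or pathologic condition that carries a high risk of bleeding (e.g. hereditary hemorrhagic telangiectasia". Section 6.3, on resuming TRC105 after a grade 1 or 2 venous thrombosis, uses nearly the same bleeding-risk phrase with a different example: "The patient does not have a pathological condition that carries a high risk of bleeding (e.g., tumor involving major vessels".

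**The concern.** Section 2.3.6.1 describes a protection that the eligibility list does not supply. Under Section 13.1 the protocol goes to health authorities and ethics committees, who would take the sentence as a description of who can enter. Sites enroll from the numbered criteria, and a patient already taking daily NSAIDs meets no named exclusion. The sponsor dealt with this group by exclusion in phase 1. Here the ulcer-history part was carried over in limited form and the medication part was not.

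For tumor site, the restart rule in Section 6.3 is more explicit than the entry rule. A site the sponsor regards as a contraindication to TRC105 is left partly to how each investigator reads a general phrase. At stake is uniform bleeding safety in patients given TRC105 with axitinib, whose own significant risks in Section 2.3.6.1 include hemorrhage. The statistical design is not at stake.

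**Working it through.** No sample-size, power or error-rate figure is involved, so the check sets the texts side by side.

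**1. Who the ulcer sentence covers, and which criterion reaches them**
- *Active or recent ulcer (within 3 months):* reached by exclusion 15, unless treated and cleared by endoscopy.
- *Ulcer history older than 3 months:* not reached by exclusion 15.
- *Current NSAID or other ulcerogenic medication, no recent ulcer:* no named criterion. Section 6.3 permits NSAIDs.
- *Any other risk factor:* only exclusion 19, which covers "Other severe acute or chronic medical (including bone marrow suppressive diseases) or psychiatric condition or laboratory abnormality that may increase the risk associated" with participation, as judged by the investigator.

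The protocol does not define ulcer risk factors. I take ulcerogenic medication to be one, because the phase 1 amendment in Section 2.3.1.3 and the prophylaxis rule in Section 6.3 both treat it that way.

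**2. Timing of the existing prophylaxis rule**
- If on-study days are counted from cycle 1 day 1, the first day beyond three in a row is day 4.
- Starting by day 1 instead brings prophylaxis forward by 4 − 1 = 3 days.
- The phase 1 bleed occurred within 5 days of the first infusion. It is one case, at another dose and without axitinib, so it informs timing only and gives no rate.
- Section 6.1.6 and Table 12 give famotidine 20 mg (or a similar H2 blocker) before each cycle 1 infusion: days 1, 4, 8, 15 and 22, which is 5 single doses in 28 days. It may stop from cycle 2 if the prior dose caused no infusion reaction. It is infusion premedication rather than daily ulcer prophylaxis, and it applies only to patients receiving TRC105.

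**3. Tumor site against the entry criteria**
- *Exclusion 9:* CNS disease, with an exception for treated, inactive, asymptomatic lesions.
- *Exclusion 11:* turns on a high risk of bleeding, whereas Section 2.3.6.1 turns on how harmful a bleed at that site would be. The two overlap but are not the same.
- *Exclusion 14:* hemorrhage or hemoptysis in the last 3 months, which screens for chest lesions that have already bled.
- *Exclusion 19:* investigator judgment.

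Together these give partial cover. None names a central-chest site or a tumor involving major vessels.

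**The case against.** The strongest reply is that the protocol already handles bleeding risk in layers. Exclusion 11 gives its example with an e.g., so the list is open, and the near-identical phrase in Section 6.3 suggests the sponsor already reads it to include major-vessel tumors. On-study NSAID use looks deliberate, since TRC105 headaches respond to it (Section 2.3.6.1), and it comes with a prophylaxis rule. Famotidine covers the infusion days of cycle 1. Section 2.3.6.1 requires monitoring for hemorrhage and a fresh risk-benefit judgment in anyone who bleeds. Section 5.2 withdraws patients with grade 3 or 4 non-CNS hemorrhage, and Section 6.2.6 interrupts axitinib for bleeding that needs intervention. Section 2.3.2.1 reports that TRC105 did not potentiate hemorrhage with bevacizumab, and the phase 1b summary in Section 2.3.4.1 mentions only grade 1 epistaxis and gingival bleeding.

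Much of this stands, and it is why the point is minor. It does not remove the ulcer mismatch: the sentence says risk factors are excluded, and they are not. The withdrawal and interruption rules act only after a bleed.

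A reader might go further and infer that the tumor-site text flatly contradicts the criteria. It does not, because Section 2.3.6.1 calls these sites a contraindication and never says such patients are excluded.

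A reader might also score how many of that section's safety statements have a matching criterion. That count would not be sound. Two sentences do point to the lists, "Patients with evidence of active coronary artery disease are excluded from participation in this trial (see exclusion criteria") and "Patients must have a platelet count of > 100,000/uL to enter this study (see inclusion criteria"), but exclusion 10 covers coronary disease only as specified events within 6 months. Likewise, exclusion 14 looks back 3 months while the text on past hemorrhage has no time limit. These are partial matches too.

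**Conclusion.** The ulcer half holds as a plain mismatch between Section 2.3.6.1 and the criteria, and it has a cheap remedy. The tumor-site half is a secondary point: a stated contraindication with partial cover that one example would make clearer.

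The documents give no share of patients with ulcer risk factors or with such tumor sites, so no count of affected patients can be stated. With 1:1 randomization of about 150 patients, 150 / 2 = 75 would be assigned TRC105, but that is the arm size and not a number at risk. For a regular NSAID user the gain is about three days of earlier cover, under the counting assumption above. The endpoint, alpha and power are unaffected.

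A reader might infer that every central-chest tumor should be a hard exclusion. The documents do not support that: the term is undefined, and the rule would remove an unknown number of patients from both arms, including controls who never receive TRC105. That is a clinical trade-off for the sponsor's physicians.

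**What to change.** 1. **Section 6.3.** Require peptic ulcer prophylaxis by cycle 1 day 1 for patients already taking NSAIDs or other ulcerogenic medication at entry. Keep the three-day rule for NSAIDs started on study.
2. **Section 2.3.6.1.** Reword the ulcer sentence so that it matches exclusion 15 and the revised Section 6.3.
3. **Exclusion 11, in the Synopsis and Section 5.1.2.** Add *tumor involving major vessels* as a second example, taken from Section 6.3. Leave any wider central-chest exclusion to the sponsor's physicians, who would first have to define it.

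The cost is amendment wording in four places (Section 6.3, Section 2.3.6.1, and exclusion 11 twice). No new assessment is needed: Section 4.1.2.1 already records medications from 28 days before treatment and requires chest imaging. The prophylaxis change excludes no one, though some patients in both arms would take an extra medication. The added example may exclude a few patients from both arms; the documents do not allow that number to be estimated.

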Figure 1:	Single-Dose and Multiple-Dose Pharmacokinetic Data from Study 105ST101	30
-----------	--	----

Table 2: Abbreviations and Specialist Terms

Abbreviation or specialist term	Explanation
ADCC	Antibody-Dependent Cell-mediated Cytotoxicity
AE	Adverse Event
AFP	Alpha Fetoprotein
AIDS	Acquired Immunodeficiency Syndrome
ALKs	Activin receptor-Like Kinases
ALT	Alanine Aminotransferase
ANC	Absolute Neutrophil Count
APA	Anti-Product Antibody
AST	Aspartate Aminotransferase
AUC	Area Under the Curve
AUC _{last}	Time of Last Measurable Concentration of Area Under the Curve
BALB/c mice	Mouse Strain
BMP	Bone Morphogenic Protein
BUN	Blood Urea Nitrogen
CABG	Coronary Artery Bypass Graft
CBC	Complete Blood Count
CEA	Carcinoembryonic Antigen
CHOP	Cyclophosphamide Hydroxydaunomycin Oncovin® Prednisone
CL	Clearance
C _{max}	Maximum Serum Concentration
CPA	Cyclophosphamide
CR	Complete Response
CRF	Case Report Form
CT	Computed Tomography
CTC	Common Terminology Criteria
dL	Deciliter
DLT	Dose Limiting Toxicity
DVT	Deep Vein Thrombosis
ECG	Electrocardiogram
ECOG	Eastern Cooperative Oncology Group
ECM	Extracellular Matrix
EGFR	Epidermal Growth Factor Receptor
ELISA	Enzyme-Linked ImmunoSorbent Assay
EOS	End of Study
FDA	Food and Drug Administration
FGF	Fibroblast Growth Factor
FU	Fluorouracil
g	Gram
GOG	Gynecologic Oncology Group
GCP	Good Clinical Practice
HACA	Human Anti-Chimeric Antibodies
HAMA	Human Anti-Murine Antibodies
Her-2	Human epidermal growth factor receptor 2

HHT-1	Hereditary Hemorrhagic Telangiectasia Type 1
HIF-1- α	Hypoxia-Inducible Factor-1- α
HIPAA	Health Insurance Portability and Accountability Act
HIV	Human Immunodeficiency Virus
HRA	Health Regulatory Authority
HUVECs	Human Umbilical Vein Endothelial Cells
ICH	International Conference on Harmonization
ID	Identification
IEC	Independent Ethics Committee
IgG	Immunoglobulin G
IgM	Immunoglobulin M
IL	Interleukin
INR	International Normalized Ratio
IP	Intraperitoneal
IRB	Institutional Review Board
i.v.	Intravenous
K _d	Avidity Binding Constant
kg	Kilogram
L	Liter
LDH	Lactate Dehydrogenase
LOQ	Limit of Quantification
μ L	Microliter
Mg	Milligram
mL	Milliliter
MACA	Monkey Anti-Chimeric Antibody
MAMA	Monkey Anti-Murine Antibody
MI	Myocardial Infarction
mm	Millimeter
MRI	Magnetic Resonance Imaging
MTD	Maximum Tolerated Dose
NCI	National Cancer Institute
NCIC	National Cancer Institute of Canada
ng	Nanogram
NHP	Nonhuman Primate
NOAEL	No Adverse Effect Level
PBS	Phosphate-Buffered Saline
PD	Progressive Disease
PDGF	Platelet Derived Growth Factor
PDGFR	Platelet Derived Growth Factor Receptor
PIGF	Placental Growth Factor
pM	Picomolar
PR	Partial Response
PSA	Prostate Specific Antigen
PT	Prothrombin Time
PTCA	Percutaneous Transluminal Coronary Angioplasty
PTT	Partial Thromboplastin Time

QA	Quality assurance
RCC	Renal cell carcinoma
RECIST	Response Evaluation Criteria in Solid Tumors
SAE	Serious Adverse Event
sCD105	Soluble CD105/endoglin
SCID	Severe Combined Immunodeficient
SD	Stable Disease
SGOT	Serum Glutamic Oxaloacetic Transaminase
SGPT	Serum Glutamic Pyruvic Transaminase
SN6j	Murine parent antibody of TRC105
sVEGFR2	Soluble VEGF Receptor 2
TGF- β	Transforming Growth Factor
TSH	Thyroid Stimulating Hormone
ULN	Upper Limit of Normal
US	United States of America
VEGF	Vascular Endothelial Growth Factor
VEGFR	Vascular Endothelial Growth Factor Receptor
VEGFR TKI	Vascular Endothelial Growth Factor Receptor Tyrosine Kinase Inhibitor

2. BACKGROUND

2.1. Angiogenesis and Cancer

Angiogenesis is required for the survival and growth of solid cancers [1, 2]. It is generally accepted that solid cancers have two phases, an avascular phase and a vascular phase [2]. During the initial avascular phase, tumors exist as small aggregates of malignant cells supported by simple diffusion of oxygen and nutrients. The progressive growth of solid cancers beyond clinically occult sizes requires the continuous formation of new blood vessels, a process known as tumor angiogenesis. Tumor growth and metastasis require angiogenesis. Therefore, inhibition of tumor angiogenesis and selective inhibition of the tumor vasculature represent potentially effective strategies for the prevention and treatment of solid cancers.

Therapies that are directed against targets implicated in the development of tumor angiogenesis are attractive for many reasons. First, except for female reproduction and wound healing, angiogenesis in adults is generally part of a pathologic process such as tumor growth or choroidal neovascularization. Second, treatments that interrupt tumor angiogenesis should apply broadly to all solid cancers. Third, angiogenic targets are present in the plasma or on endothelial cells themselves. These targets are readily accessible to antibody treatments, in contrast to targets expressed within tumors that are more difficult for antibodies to access. Fourth, angiogenic targets on vascular endothelial cells are less prone to genetic mutation than targets expressed by genetically unstable cancer cells. As a result, development of resistance may be more predictable for agents that target endothelial cell functions than for those targeting cancer cells.

Indeed, agents that target pathways required for tumor angiogenesis have an important role in the therapy of cancer patients. The monoclonal antibody bevacizumab, which binds to the angiogenic cytokine VEGF, significantly prolongs overall survival for patients with advanced colorectal cancer or non-small cell lung cancer when added to standard chemotherapy regimens [3, 4]. Bevacizumab is also effective therapy for renal cell cancer and malignant glioma [5-7]. Orally available small molecule VEGF inhibitors include sunitinib, sorafenib, pazopanib, and axitinib, which have been shown to prolong survival in patients with metastatic renal cell cancer, hepatocellular cancer, sarcoma and colorectal cancer [8-11].

